14.4 Stopping or Early Assessment

Consideration will be given to earlier assessment at say 200 events where there is evidence that the prevalence estimates for each type of pathogen above are out by more than 50%.

14.5 Statistical Methods

14.5.1 Primary Outcomes

The outcome data from each testing device will be compared against its paired standard to produce 2 x 2 tables for each type of disease

Disease +ve Disease -ve

	Standard positive	Standard negative
Test positive	True Positive (TP)	False Positive (FP)
Test negative	False Negative (FN)	True Negative (TN)

From this we calculate:

i. Sensitivity, Specificity

Sensitivity is the percentage of cases that had the observed outcome was correctly predicted by the model (i.e., TP/(TP+FN).

Specificity is the percentage of observations that were also correctly predicted as not having the observed outcome (i.e., TN/FP+TN).

- ii. Positive Predictive Value
- iii. Negative Predictive Value
- iv. Likelihood Ratios (LR+ / LR-) for the strength of the test versus standard
- v. Accuracy and Cohen Kappa (for agreement)
- vi. If data allows, we intend to model some ROC curves around the various clinical thresholds to ascertain the best use model for this device in this clinical setting.

These core calculations and tests will be performed using JASP software on the recorded data sets.

vii. McNemar's test to compare sensitivity/ specificity.

McNemar's test will be used to assess paired differences in positive and negative results between the new POCT and the established gold standard test for each of the four shared respiratory infections. This test focuses on cases where the two tests disagree, quantifying whether the new test detects significantly more or fewer positive results than the comparator.

For example, among patients tested for RSV, if the new test identifies more positive cases than the gold standard, and this difference is statistically significant on McNemar's test (p < 0.05), this may indicate **superior sensitivity**. Results will be reported with the test statistic, degrees of freedom, and p-value. A similar analysis will be repeated for each infection, supporting the primary endpoint of diagnostic accuracy.

McNemar tests the **null hypothesis** that both tests have the same proportion of positive results by evaluating a test statistic and comparing this with a Chi squared distribution statistic if the value is lower then the null hypothesis is proved.

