9.0 STUDY OBJECTIVES

9.1 Primary Objective

The primary objective of the study is to demonstrate that the Logicore System multiplex 6 panel respiratory pathogens point of care testing device has increased diagnostic sensitivity when compared to the current gold standard POC multiplex panel at CUH Trust whilst maintaining accuracy, including Positive Predictive Value (PPV), Negative Predictive Value (NPV) and specificity.

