14.2.4 Cost Benefit Analysis

We will evaluate the health economic implications of using the new POCT device to detect two additional pathogens earlier in the patient's care pathway. In the current clinical pathway patients with negative results on the standard test and ongoing symptoms may undergo delayed or reflex laboratory testing to identify other infections, including pathogens targeted by the new test. By enabling earlier diagnosis and treatment at the point of care, the new test may reduce time to treatment, avoid unnecessary empirical therapies and improve resource utilisation. This component will be assessed through a within-trial cost effectiveness analysis using trial data to compare diagnostic pathways and estimate cost per additional case detected, cost per timely treatment initiated and incremental cost-effectiveness ratio (ICER).

The overall hypothesis is that the new test will demonstrate superior sensitivity for RSV based on preliminary data and known limitations of the current test and show the added benefits of the earlier diagnosis on the hospital costs and prescribing.

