14.3.1 For Sensitivity (or Specificity)

$$n=(Z^2.P.(1-P))/d^2$$

n = number of diseased (or non-diseased) subjects required

Z = 1.96 for 95% confidence (the assumption is that this approach could apply to either sensitivity or specificity but here we expect sensitivity will require the higher resolution)

P = expected sensitivity (or specificity) (0.95) for two tailed test

d = desired precision (0.10)

Samples needed for positive cases (sensitivity):

n = 18.2 >>> 19 cases.

From our above table our minimum expected prevalence for any one type of disease is 5% and our maximum is 15% so we can easily estimate what sample total will most likely deliver 19 cases.

If prevalence is low:

N = n/prevalence = 19/.05 = 380 cases.

If the prevalence is uniformly high:

N = n/prevalence = 19/.15 = 127 cases.

This gives us a range of sample size which allows for this variable prevalence. If we assume the worst prevalence state, then 380 cases are required and a further 20 might provide additional safety to achieve a 19-event incidence for each type of infection.

Thus, the recommendation is for a trial recruiting **400** participants.

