14.6 Estimand Table

Objective	Treatment / Strategy	Population	Variable (Outcome)	Intercurrent Events	Summary Measure (Estimand)
Primary: Compare diagnostic sensitivity and accuracy of new POCT vs gold standard for 4 respiratory infections	New POCT vs v gold standard POCT	symptoms meeting	Diagnostic test result (positive/negative) per pathogen	- Invalid swab or test - Withdrawal before testing - Gold standard indeterminate	Difference in sensitivity and specificity; 95% CIs for each; McNemar's test for paired comparisons
Secondary 1: Compare turnaround time from swab to result	New POCT vs gold standard POCT	Same as above	Time (minutes) from sample collection to result availability	- Missing timestamps Result delayed due to user error or system failure	- Mean/median time per method; Paired t-test or Wilcoxon signed-rank test
Secondary 2: Compare specificity of new POCT vs gold standard	Same as above	Same as above	Diagnostic result per pathogen in gold standard negative patients	- Invalid test - Patient lost to follow-up	Specificity per infection type; 95% CI
Secondary 3 & 4: Estimate PPV and NPV of new POCT	New POCT	Same as above	PPV = TP/(TP+FP); NPV = TN/(TN+FN)	- Inconclusive reference test result	PPV, NPV per infection; descriptive analysis with 95% CI
Secondary 5: Assess patient acceptability of new test	New POCT	Patients providing questionnaire data	Self-reported scores on comfort, experience, willingness to retest	- Non-response - Incomplete questionnaire	Median scores; frequencies; thematic analysis for free text

CONFIDENTIAL

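### The protocol states two different superiority hypotheses and tests four pathogens without saying which, or how many, must succeed

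*Protocol*

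**What the plan says.** Section 9.1 sets the primary objective at the level of the device, which is to show that it "has increased diagnostic sensitivity when compared to the current gold standard POC multiplex panel at CUH Trust". No pathogen is singled out.

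Section 14.2.4, under the cost-benefit heading, states a different hypothesis: "The overall hypothesis is that the new test will demonstrate superior sensitivity for RSV based on preliminary data".

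Section 14.5.1 plans McNemar's test "for each of the four shared respiratory infections", namely Flu A, Flu B, RSV and SARS-CoV-2. Its worked example is RSV: if the new test finds more positives and "this difference is statistically significant on McNemar's test (p < 0.05), this may indicate" superior sensitivity. The method is then extended to the other pathogens: "A similar analysis will be repeated for each infection, supporting the primary endpoint of diagnostic accuracy". The section describes the test as "quantifying whether the new test detects significantly more or fewer positive results than the comparator", which implies a two-sided test, and it refers the statistic to a chi-squared distribution.

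The estimand table (14.6) gives the primary summary measure as "Difference in sensitivity and specificity; 95% CIs for each; McNemar's test for paired comparisons". It contains no rule for combining the four results.

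**The concern.** A device-level claim needs a rule that turns four pathogen-level tests into one conclusion, and the protocol gives none. It also has two candidates for the confirmatory hypothesis, one broad and one confined to RSV, and does not rank them. A final report could therefore claim the primary objective on RSV if RSV is significant, or on another pathogen if that one is.

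The study's conduct makes later selection a practical matter. The sponsor reviews data as they accrue (16.8) and analyses the final data (16.10), and section 14.1 accepts that blinding will be difficult. At stake is the error rate behind any statement that Logicore is more sensitive than the current test.

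**Working it through.** **1. The plan's own figure.** Section 14.3.1 uses n = Z²P(1−P)/d² with Z = 1.96, P = 0.95 and d = 0.10. This gives 3.8416 × 0.0475 / 0.01 = 18.25, rounded up to 19 positives. At the lowest prevalence (Flu B, 5%), 19 / 0.05 = 380, and 20 extra make 400. The figure reproduces. Although the section describes the input as "P = expected sensitivity (or specificity) (0.95) for two tailed test", this is a precision calculation for one proportion. It contains no power and no alpha for the McNemar comparisons, so it does not supply the missing rule.

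**2. Error rate if any one of four may carry the claim.** Inputs: four tests (14.5.1), nominal two-sided 5% each (the RSV example, carried to the others), no true difference, independence assumed.
- At least one false result in Logicore's favour: 1 − 0.975⁴ = 9.6%, against 2.5% for one test.
- At least one false result in either direction: 1 − 0.95⁴ = 18.5%, against 5%.
- Without assuming independence, the upper bounds are 4 × 2.5% = 10% and 4 × 5% = 20%.

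**3. Behaviour of the chi-squared test with few discordant pairs.** The documents do not give the number of discordant pairs. Prevalences of 5% to 15% in 400 participants give 20 to 60 positives per pathogen, and 95% sensitivity leaves about 1 to 3 missed by Logicore. The number positive on Logicore alone is not stated. As an assumption, take m = 3 to 10 discordant pairs, split by chance under the null, with rejection when (b−c)²/m exceeds 3.84 (uncorrected) or when the exact binomial p is below 0.05.

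| m | Splits rejected, uncorrected | Two-sided size, uncorrected | Two-sided size, exact |
|---|---|---|---|
| 3 | none | 0% | 0% |
| 4 | 4–0 | 2/16 = 12.5% | 0% |
| 5 | 5–0 | 2/32 = 6.25% | 0% |
| 6 | 6–0 | 2/64 = 3.1% | 3.1% |
| 7 | 7–0 | 2/128 = 1.6% | 1.6% |
| 8 | 8–0, 7–1 | 18/256 = 7.0% | 0.8% |
| 9 | 9–0, 8–1 | 20/512 = 3.9% | 3.9% |
| 10 | 10–0, 9–1 | 22/1024 = 2.1% | 2.1% |

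A 4–0 split gives p = 0.046 by uncorrected chi-squared and 0.125 by the exact test. The uncorrected size moves above and below 5% as m changes; the exact size never exceeds 5%.

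**4. Steps 2 and 3 together.** Assume the number of discordant pairs per pathogen is Poisson with a mean between 4 and 20. The four-test error in Logicore's favour is then about 8% to 10% with the uncorrected form and about 1% to 6% with the exact test (both directions: about 16% to 19% and 2% to 11%).

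**5. What adjustment requires.** The first Holm step uses 0.05 / 4 = 0.0125. With all discordant pairs in one direction, the exact p is 2 × 0.5^m: 0.031 at m = 6, 0.0156 at m = 7 and 0.0078 at m = 8. The minimum is therefore 8 pairs instead of 6.

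**The case against.** The strongest reply is that the any-one-of-four rule is inferred. The threshold appears once, inside an example about RSV, and the wording is tentative. No section says that one significant pathogen establishes the device-level objective. Section 14.1 frames the sensitivity goal pathogen by pathogen. If four separate claims are meant, each keeps its own 5%, and if all four must succeed, no adjustment is needed. This stands: a reader might infer that the primary claim has an 18.5% type I error, but the documents do not support that as a fact. That figure also counts results against Logicore, which cannot support increased sensitivity.

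A reader might also infer that the chi-squared test always rejects too often here. That is not supported either. The number of discordant pairs is unknown, the inflated sizes in the table are isolated peaks, and the protocol does not say whether a continuity correction applies. With the correction, size is 0% at 4 pairs and 0.8% at 8. The exact test alone also removes much of the inflation, as step 4 shows.

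Finally, a separate analysis plan might supply the rule. But section 14 is itself headed as the statistical analysis plan and already fixes the tests and the threshold. A later document would still have to resolve the conflict between 9.1 and 14.2.4. The reply limits the size of the problem; it does not remove the conflict or the missing rule.

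**Conclusion.** The point holds in a limited form. Sections 9.1 and 14.2.4 state different superiority hypotheses, and section 14.5.1 tests four pathogens in support of the primary endpoint without a success rule. This leaves the confirmatory hypothesis open to choice after the results are known.

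If one significant pathogen were allowed to carry the device-level claim, the relevant nominal error is about 9.6% against 2.5%, assuming independence and tests that attain their nominal level. For the chi-squared McNemar test the supportable criticism is erratic size: between 0% and 12.5% over an assumed 3 to 10 discordant pairs.

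Nor do the documents oblige the sponsor to make RSV the sole confirmatory test. Section 14.2.4 points that way, but the preliminary data it mentions are not shown, and 400 was set so that the rarest pathogen is covered. Whether finding more positives than the reference test means greater sensitivity is a separate question that this point does not settle.

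**What to change.** Reconcile 9.1, 14.2.4 and 14.5.1, and state one success rule before data are seen:

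- **(a) One named comparison** at two-sided 5% (RSV, if 14.2.4 is the intended hypothesis). Report the other three pathogens as estimates with 95% confidence intervals, and reword 9.1 to match. Cost: no confirmatory claim for three pathogens, and a narrower primary objective.
- **(b) Any of the four may support the claim**, with Holm's procedure. Cost: the first step needs at least 8 one-directional discordant pairs instead of 6.
- **(c) All four must succeed**, with no alpha adjustment. Cost: lower power, since with the exact test each pathogen needs at least 6 discordant pairs even if all favour Logicore.

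Under any of these, specify the exact McNemar test and move the hypothesis sentence from the cost section to the objectives. The planned 400 rests on precision and is unaffected by the choice, but the power of the chosen rule remains unstated. The cost in effort is a revision of the text; choosing the rule is a substantive decision for the sponsor.

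### The McNemar rule takes a significant excess of Logicore positives as possible superior sensitivity, which the test cannot show, and calls a non-significant result proof of the null

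*Protocol*

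**What the plan says.** The primary objective (Protocol section 9.1) is to show that Logicore "has increased diagnostic sensitivity when compared to the current gold standard POC multiplex panel", while accuracy is maintained. Section 14.2.4 adds: "The overall hypothesis is that the new test will demonstrate superior sensitivity for RSV".

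McNemar's test is the only significance test named for this comparison (sections 14.2.1, 14.5.1 and 14.6). Item vii of section 14.5.1 lists it as comparing sensitivity and specificity. The null hypothesis given there is "that both tests have the same proportion of positive results by evaluating a test statistic". Two rules follow:

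- **Significant result.** In an RSV example, "if the new test identifies more positive cases than the gold standard, and this difference is statistically significant" at p < 0.05, superior sensitivity may be indicated. The analysis is repeated for each of the four shared infections.
- **Non-significant result.** The statistic is compared with a chi-squared value, and "if the value is lower then the null hypothesis is proved".

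The 2x2 table in the same section takes Cepheid as the standard. Every Logicore-positive, Cepheid-negative result falls in the false-positive cell.

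**The concern.** The heading of item vii and its null hypothesis describe different comparisons. Sensitivity is compared among people who have the infection, and specificity among those who do not. A test of equal positivity on everyone mixes the two. A Logicore-only positive may be a case that Cepheid missed or a false alarm, and McNemar's test counts both the same way. The section also contradicts itself: results that its table labels false positives become, when there are enough of them, a sign of better sensitivity.

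With Cepheid as the standard, its sensitivity is 100% by construction. The sensitivity difference planned in section 14.6 therefore cannot favour Logicore, and the McNemar sentence is the only route in section 14.5.1 to the superiority that the objective seeks.

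The second rule is wrong whatever the data. Failure to reject does not establish equality, and the protocol gives no equivalence or non-inferiority margin that would support such a conclusion. What is at stake is that a less specific Logicore could be described as possibly more sensitive, and a less sensitive one as proven equal.

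**Working it through.** **The plan's own figures (section 14.3.1).** n = 1.96² × 0.95 × 0.05 / 0.10² = 18.25, rounded up to 19. Then 19/0.05 = 380 and 19/0.15 = 126.7, or 127; recruitment is set at 400. These reproduce. They are precision figures and imply no power for McNemar's test. With 400 participants the expected positives are 400 × 0.05 = 20 for Flu B and 400 × 0.15 = 60 for RSV.

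**Notation.** b = Logicore-positive, Cepheid-negative; c = Logicore-negative, Cepheid-positive. The protocol does not say which version of the test applies, so three were run, two-sided at 0.05:

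- uncorrected: (b − c)²/(b + c), against 3.84
- continuity-corrected: (|b − c| − 1)²/(b + c), against 3.84
- exact: 2 × P(Bin(b + c, ½) ≤ min(b, c))

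**How few false positives suffice.** With c = 0 the uncorrected statistic equals b, so b = 4 gives p = 0.046. With b = 6 the exact p is 2 × 0.5⁶ = 0.031, and the corrected statistic is 25/6 = 4.17, p = 0.041. Six false positives among the 340 RSV-negative participants is a specificity of 334/340 = 98.2%.

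**Significant result without better sensitivity.** Assumptions: N = 400, Cepheid is the truth, RSV prevalence 15%, Logicore misses 5% of positives. Logicore is then the less sensitive device, and any result in its favour misleads. In each trial (b, c) is trinomial with probabilities 0.85 × FP and 0.15 × 0.05. The expected c is 60 × 0.05 = 3. The false-positive rate (FP) is not given in the protocol and is shown as a range.

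| Logicore FP rate | Expected b (340 × FP) | Chance of a significant result favouring Logicore |
|---|---|---|
| 1% | 3.4 | 1-3% |
| 2% | 6.8 | 14-21% |
| 3% | 10.2 | 40-51% |
| 4% | 13.6 | 68-78% |
| 5% | 17.0 | 87-92% |

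The ranges span the three versions of the test. A second model does not take Cepheid as truth: both sensitivities are 0.95 and conditionally independent, and Cepheid's specificity is 1.00. For RSV it gives 11-18% at Logicore specificity 0.99 and 39-48% at 0.98. With Cepheid's specificity at 0.995 and Logicore's at 0.98 it gives 19-26%.

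**Non-significant result with a real deficit.** Assume Cepheid as truth, and that Logicore misses 15% of cases and has no false positives. Then b = 0, and significance needs c ≥ 4 (uncorrected) or c ≥ 6 (exact or corrected).

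- Flu B: c ~ Bin(400, 0.05 × 0.15 = 0.0075). P(c ≤ 3) = 0.65 and P(c ≤ 5) = 0.92.
- RSV: c ~ Bin(400, 0.15 × 0.15 = 0.0225). P(c ≤ 3) = 0.02 and P(c ≤ 5) = 0.11.

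So the null would be called proved in 65-92% of trials for Flu B and 2-11% for RSV. Under the second approach, with 19 diseased participants and independent true sensitivities of 0.95 and 0.85, power is 2-14%.

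**The case against.** The strongest defence is that the protocol is more careful than a quick reading suggests and already plans much of what is needed.

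- A reader might infer that any excess of Logicore positives counts as superiority. It does not: section 14.5.1 requires p < 0.05, offers the case as an example and says only that it may indicate superior sensitivity. This stands and limits the point to significant excesses. The hedge does not tell the reader that false positives are the competing explanation.
- A reader might infer that a non-significant McNemar result is how maintained accuracy will be judged. Nothing says so. Sections 9.1 and 10.1 tie accuracy to PPV, NPV and specificity, and sections 14.5.1 and 14.6 report these separately.
- The 2x2 tables already give positive and negative agreement with Cepheid and both discordant counts, and section 14.6 adds 95% confidence intervals. A false-positive rate of 3-5% would appear as a specificity of 95-97% beside the p-value. This stands as mitigation, but it leaves the two McNemar statements uncorrected.
- Section 11, item C, sends Logicore-only positives to second-line PCR and reclassifies them by its result. This helps only in part. The step applies only if symptoms persist and policy requires testing. Cepheid-only positives are classed as Logicore false negatives without a further test (item A). The McNemar text does not use the second-line result.
- The size depends on assumed error rates. At a 1% false-positive rate the misleading RSV result is rare, and for RSV a 15% miss rate would usually be detected.

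**Conclusion.** The point holds in this form. Section 14.5.1 contains one statement that is wrong outright (non-significance as proof of the null) and one inference that the test cannot support (a significant excess of positives as possible superior sensitivity). Both concern the primary comparison.

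The risk of a misleading RSV result rises from 1-3% at a 1% false-positive rate to 87-92% at 5%. Calling the null proved despite a 15% miss rate is mainly a problem for Flu B (65-92%) and much less so for RSV (2-11%). These figures rest on N = 400, the protocol's prevalences, Cepheid as truth and assumed Logicore error rates. The two logical faults do not depend on them.

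Because section 14.2.4 names RSV, a reader might also infer that any superiority claim should be confined to RSV. The documents do not support that as a correction: the primary estimand in section 14.6 covers four infections, the RSV sentence sits in the cost-benefit section, and narrowing the claim is the sponsor's choice.

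**What to change.** In section 14.5.1, before any results are seen:

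1. Replace "if the value is lower then the null hypothesis is proved" with a statement that the null hypothesis is not rejected and the result is inconclusive.
2. State that McNemar's test on all participants compares positivity rates. Report the paired difference in positivity with its 95% confidence interval and the discordant counts in each direction.
3. Interpret that result beside the positive and negative agreement with Cepheid already planned in sections 14.5.1 and 14.6.
4. Base any statement of superior sensitivity only on Logicore-only positives confirmed by the second-line PCR of section 11, item C, and say that this verification is conditional and runs in one direction.
5. Bring the primary row of the estimand table in section 14.6 into line, since a sensitivity difference against a Cepheid standard cannot favour Logicore.

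The cost is a few sentences and slightly more analysis output. No extra participants or swabs are needed.
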